Adult patients who have undergone deceased donor liver and/or kidney transplantation will be recruited and randomized 1:1 to standard of care physician-guided dosing or PPM-guided dosing. Patients with contraindications to tacrolimus will be excluded. Following transplantation, patients will be started on a standard of care medication regimen including tacrolimus. For the first 72 hours tacrolimus will be dosed per standard of care. This allows enough data points to be gathered to allow PPM prediction. Blood tacrolimus trough levels will be taken daily. For standard of care subjects, a senior clinical pharmacist will determine the subsequent doses in consultation with the attending surgeon on call. For PPM subjects, de-identified data consisting of the daily treatment regimen details including drugs already administered, drugs to be administered, and hemodialysis or any other procedures to be performed will be sent to the PPM team at UCLA. Following analysis, the PPM team will suggest a tacrolimus dose for clinician (attending surgeon on call) approval prior to administration. In the rare instance that the UCLA team cannot arrive at a recommendation, then the subject will receive the standard of care (physician-guided) tacrolimus dose. Patients will remain on the trial until discharge from the hospital at which point they will all revert to standard of care dosing. Outcome measures will include i) fraction of days outside of target range, ii) fraction of days with large (> 2 ng/mL) deviations, and iii) ratio of area-under-the-curve outside of target range to total. Clinical safety and efficacy measures will also be monitored to ensure subject safety and to correlate trough level maintenance to clinical outcomes. These include adverse events such as neurotoxicity [documented seizures, clinically significant tremors, or imaging-confirmed posterior reversible encephalopathy syndrome (PRES)], nephrotoxicity (biopsy proven acute kidney injury or calcineurin toxicity, anuria or oliguria requiring dialysis), biopsy-proven rejection, need for repeat steroid pulse, graft loss, or death.

Statistical Analysis. Comparative analysis of the effectiveness of PPM dosing will be assessed using area-under-the-curve and variance analysis as in sub-aim 1 above. Based on our preliminary results thirty patients per group will provide greater than 90% power ($\alpha = 0.05$) to show a difference in a two-tail test.

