Feasibility, Anticipated Challenges and Proposed Solutions. The UF transplant program performs more than 150 adult liver and/or kidney transplant operations per year. This allows us to complete recruitment in less than 6 months. We do not anticipate major challenges; [name] has substantial experience working on the clinical validation of PPM. We have already successfully performed a prospective pilot study with the same protocol. Because of this we have an established protocol that is conducive to markedly improving the treatment outcomes of patients that participate in the study.

Sub-Aim 2: Comparing the pharmacokinetics of patients with high variance in tacrolimus dosing with those with low variance.

Studies in kidney transplant recipients have indicated that cytochrome P450 CYP3A5 genotype and hematocrit account for more than 60% of variability in tacrolimus pharmacokinetics. Data in liver transplant patients is less well characterized but the unexplained variability is likely higher. To examine contributors to variance in tacrolimus dosing, we will measure tacrolimus pharmacokinetics in this study and correlate the findings with donor/recipient genetics, changes in drug regimens, and clinical factors such as liver and kidney function. For each subject, at least three blood samples (pre-dose and 2 and 6 hours after the dose) will be collected on study days 2, 7, and 14. We will use these pharmacokinetic data to interpret the performance of PPM predictions and provide additional validation for our trial. Genotyping of each donor and recipient

will be performed for CYP3A5 and P-glycoprotein to look for their contribution to variance in pharmacokinetics. Both one- and two-compartment models will be evaluated.

Statistical analysis. Similar to the previous sub-aim, comparisons between the two groups will be performed using either the two-tailed Welch's t-test or Student's t-test. For nonparametric (non-normal) distributions, a two-tailed Levene's test will be used to compare variances, and a two-tailed Wilcoxon Rank Sum test will be used to compare medians. The number of subjects in this study is similar to that in the study by Gerard et al in their approach to building a model for determination of tacrolimus trough blood concentrations.

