Data Safety Monitoring Plan. The Principal Investigator (PI) will be responsible for ensuring participants' safety on a daily basis. Given the low risk status of this study with minimal impact on patient care, a Data and Safety Monitoring Board will not be required. Furthermore, each liver/kidney transplant patient is closely followed by a large group consisting of the clinical transplant team (surgeons, hepatologists, pharmacist, nurse coordinators) and the transplant administrative team (transplant program managers and quality officers). One-month, one-year, and three-year outcomes are monitored closely and reporting on patient quality is mandated by the United Network for Organ Sharing (UNOS). Dedicated statisticians in the transplant program monitor real-time outcomes and report them in weekly emails and monthly quality meetings.

A Data Safety Monitoring Board will additionally be appointed. It will include a transplant hepatologist, a transplant nephrologist, and a biostatistician not involved in the study. We will perform an interim analysis comparing the occurrence of i) biopsy-proven rejection episodes, and ii) fraction of days with large (> 2 ng/mL) deviations after ten patients have been randomized into each arm (twenty total subjects). The board will meet after enrollment of 10 patients into each arm (to evaluate the interim analysis) and then every six months thereafter until study completion. The study will be stopped in the event there is a significant unacceptable difference between the two groups. The biostatistical consulting service at the CTSI will assist in monitoring study enrollment, safety signals, and achievement of targets.

Protection of patient medical records: To ensure that patient information is de-identified/anonymized, we will abstract all data (images, lab, clinical data etc.) onto a page or file with only the anonymization codes with no personal identifiers or utilize protocols/programs that will be able to redact the personal identifiers when uploading them as data for study. The code key will only be available to the Project PI and authorized personnel and kept in a secure, locked location. Upon completion of the study, this coded template/anonymization key will be discarded according to regulations. The PI will oversee this task.

POSSIBLE DISCOMFORTS AND RISKS:

Risks of PPM-guided dosing of therapeutic agents to optimize patient-specific immunosuppression include:

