- The administration of a drug dose that varies from those given based on clinical practice. This may result in over-dosing or under-dosing. The risks of chronic over-dosing include altered mental status and renal injury. The risks of chronic under-dosing include possible rejection. Both of these risks are mitigated by the fact that blood drug levels are tested daily and deviations will be corrected.
- For Sub-Aim 2, additional blood draws will need to be performed (2 and 6 hours after the dose), on postoperative days 2, 7, and 14. (The pre-dose blood draw is standard of care.)

- Patient medical records will need to be accessed during the study. Therefore, there is a risk of exposure of PHI. Patient-record access and subsequent anonymizing and de-identification of records will be implemented (as indicated above).

Protection Against Risks: The PPM process is not automated. PPM-suggested doses are always based on implicit limits set by the clinical team so that doses will always be within clinically-relevant levels. Most importantly, the administered dose will always be selected by the supervising physician following consultation with the PPM team.

The blood draws will be performed by trained phlebotomists and will not exceed 7 mL per blood draw for a total of 42 mL over two weeks at maximum.

POSSIBLE BENEFITS:

The subjects themselves may or may not benefit from being part of this study. The PPM process has the potential to optimize tacrolimus dosing for the patients on the treatment arm. For the population at large, the ability to definitively optimize dosing will enable the accurate correlation of genomic factors with dosing trends. This may ultimately help eliminate health disparities in not only transplantation but other indications as PPM is broadly applicable and scalable.

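### If recruitment finishes in under 6 months as projected, the board's second scheduled meeting falls after enrolment ends, so up to 40 of 60 patients enrol after its only scheduled comparison that can affect enrolment (minor)

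*Combined protocol and SAP*

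**What the plan says.** All references are to the combined protocol and SAP.

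- **Size.** The statistical analysis paragraph of Sub-Aim 1 plans thirty patients per group, randomised 1:1, so 60 in all.
- **Recruitment.** Feasibility, Anticipated Challenges and Proposed Solutions gives a volume of more than 150 transplants a year and concludes: "This allows us to complete recruitment in less than 6 months".
- **Board schedule.** The Data Safety Monitoring Plan first says that a board is not required and then appoints one. It is to meet "after enrollment of 10 patients into each arm (to evaluate the interim analysis) and then every six months thereafter until study completion". The interim analysis compares biopsy-proven rejection and the fraction of days with large trough deviations. No pause in enrolment and no ad hoc meeting is described.
- **Criterion.** "The study will be stopped in the event there is a significant unacceptable difference between the two groups".
- **End of PPM dosing.** Sub-Aim 1: "Patients will remain on the trial until discharge from the hospital at which point they will all revert to standard of care dosing".
- **Other safeguards.** The Data Safety Monitoring Plan describes daily oversight by the principal investigator, weekly and monthly outcome reports by the programme's statisticians, and help from the CTSI biostatistics service with safety signals. Under Protection Against Risks, "the administered dose will always be selected by the supervising physician following consultation with the PPM team".

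**The concern.** The first board meeting is set by a patient count and later ones by the calendar. In a trial that recruits quickly, six-month spacing can pass over the rest of enrolment. The board would then compare the arms once, on the first 20 patients, and next meet when no one is left to enrol. PPM-guided dosing stops at discharge, so unless a stay lasted about 2 months or more, that dosing would be over too.

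At stake is whether a scheduled independent comparison of rejection by arm can influence the later part of the trial. The protocol's own risk section lists rejection as a possible consequence of under-dosing.

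**Working it through.** **Inputs.** From the documents: 60 patients; more than 150 transplants a year; recruitment in under 6 months; first meeting at 20 patients; next meeting six months later. Assumed: even accrual, and all rejection rates, since the documents give none.

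**The plan's recruitment figure.** 60 / 150 × 12 = 4.8 months if every transplant recipient is enrolled. Finishing in 6 months needs 60 of 75, or 80%. The projection is arithmetically possible at the stated volume.

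**Meeting dates.** With accrual over T months, the first look is at T/3 and the second meeting at T/3 + 6. The second falls at or after the end of enrolment when T/3 + 6 ≥ T, that is, T ≤ 9.

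| T (months) | First look | Second meeting | Enrolled by second meeting | 40th patient enrolled (2T/3) |
|---|---|---|---|---|
| 4.8 | 1.6 | 7.6 | 60 (2.8 months after the last) | 3.2 |
| 6 | 2.0 | 8.0 | 60 (2.0 months after the last) | 4.0 |
| 9 | 3.0 | 9.0 | 60 (same time as the last) | 6.0 |
| 12 | 4.0 | 10.0 | 50 | 8.0 |
| 18 | 6.0 | 12.0 | 40 | 12.0 |

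At 12 months, 30 of 60 enrol between the two meetings. A review at 40 patients would come 2 months earlier than the scheduled one, against 4 months earlier when T = 6. At 18 months the two dates coincide. Recruiting in 9 months needs 60 of 112.5 transplants, about 53%.

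**Patients still to enrol at the first meeting.** Counted from the trigger, 60 − 20 = 40. If the meeting lags and enrolment continues at 10 to 12.5 a month, a lag of 0.5 month leaves 40 − 5 = 35 to 40 − 6.25 = 33.75. A lag of 1 month leaves 30 to 27.5. The range is about 28 to 35.

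**What an earlier second look could detect on rejection.** The plan names no test. For illustration I use Fisher's exact test, one-sided for harm at p<0.05 at each look, with exact binomial probabilities.

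| Rejection, control v PPM (assumed) | One look, 10 per arm | Looks at 10 and 20 evaluable per arm | Looks at 10 and 16 evaluable per arm |
|---|---|---|---|
| 10% v 30% | 14% | 37% | 27% |
| 10% v 40% | 29% | 64% | 51% |
| 5% v 15% | 3% | 10% | 6% |

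The last column matters because 40 enrolled is not 40 discharged. Sixteen per arm means 40 − 32 = 8 patients still in hospital, which at 10 to 12.5 enrolments a month is an average stay of about 0.6 to 0.8 month. That stay is also an assumption.

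**False flags**, from one look to looks at 10 and 20 per arm, same test: 0.5% to 1.1% (10% in both arms), 1.5% to 3.2% (20%), 1.9% to 3.8% (30%).

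**The case against.** **The projection may be optimistic.** It rests on one feasibility sentence, needs 80% or more of 150 transplants a year, and entry is limited to deceased-donor recipients without contraindications to tacrolimus. This stands, and makes the point conditional. It does not remove it, because the plan should work on its own timetable.

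**Patients are watched in other ways.** A reader might infer that patients enrolled after the first 20 go without safety monitoring. The documents do not support that. Troughs are taken daily, the principal investigator oversees safety, the programme and the CTSI service monitor outcomes, and a physician selects every dose. What is missing is narrower: none of these is described as comparing rejection between arms.

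**Forty is a ceiling.** Correct. It counts from the trigger, and a lag in the meeting reduces it.

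**The gain may be small.** Also correct. Follow-up within the trial ends at discharge, so rejection could be rare, and at 5% v 15% even two complete looks flag only 10% of the time. The gain also includes a second unadjusted test. The first look compares trough deviations as well, which may be more sensitive than rejection; the plan gives no effect size from which to judge that.

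**The stopping sentence.** A reader might infer that it has no direction and is unusable, or that it means p<0.05. Neither is supported. The word unacceptable points to harm, and board judgement is a legitimate reading in a 60-patient study that the plan calls low risk. The absence of a named arm, test or threshold is mainly missing detail.

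**Conclusion.** The schedule point holds on the plan's own figures. With recruitment in under 6 months and even accrual, the second meeting falls at least 2 months after the last enrolment. Up to 40 of 60 patients, or about 28 to 35 with a lag of 0.5 to 1 month, enrol after the only scheduled board comparison that can affect enrolment. It holds up to 9 months of accrual, is weaker at 12 and is gone at 18.

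It is a minor point, worth making because the change is cheap. It does not show that the trial is unsafe or that the stopping rule is invalid. The benefit for detecting excess rejection ranges from modest to slight, depending on rates the documents do not give and on how many patients are evaluable at the second look.

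**What to change.** In the Data Safety Monitoring Plan:

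- Hold the second board review after 40 subjects are enrolled or six months after the first review, whichever comes first, and six-monthly after that.
- Hold the first review when 10 per arm have been discharged. Base each comparison on discharged patients and state how many are evaluable. As written, the look is triggered by randomisation, and tacrolimus is dosed per standard of care for the first 72 hours, so the newest PPM patients could have little or no PPM exposure.
- State that the review is for harm in the PPM arm and is advisory to the board.

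**Cost.** One existing meeting moves earlier and a few sentences change; no patients or procedures are added. The first look comes later by about one hospital stay, which narrows the gap between the two looks. False flags rise slightly: if one-sided p<0.05 were used at both looks with 20 evaluable per arm at the second, to 1.1% to 3.8% in total for rejection rates of 10% to 30% in both arms. Each would prompt a board discussion, not an automatic stop.
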